12.2. Baseline Values

Unless otherwise noted, baseline is defined as the last non-missing value recorded prior to the first dose of trial drug. Unscheduled visits will be used in the determination of baseline values, when applicable. This also applies to the primary efficacy variables derived from the VMS data collected in the subject diary, but on a weekly basis as described in the definition of the primary efficacy variables.

12.3. Handling of Dropouts or Missing Data

For days with missing VMS diary information, the number and intensity of VMS will be imputed with the mean values of the remaining days of the respective 7-day period, but only if at least 4 days with VMS data in this 7-day period are available. Otherwise, no calculation of the primary and related secondary efficacy variables will be done for this period.

No method of imputation is planned for the primary efficacy variable analysis since an MMRM model is used. As previously stated, sensitivity analyses of the primary efficacy variables may resort to imputation of missing data in order to assess the robustness of the MMRM results.

12.4. Primary Efficacy Variables

The weekly frequency of moderate to severe VMS at baseline, week 4 and week 12, respectively, is defined as the total number (sum) of all recorded moderate to severe VMS experienced during the last 7 consecutive days during the Screening period, days 22 to 28 (week 4) and days 78 to 84 (week 12), respectively.

The mean severity score of VMS is defined as the arithmetic mean of the daily severity score values of VMS (moderate or severe) observed from days -7 to -1 at baseline and the arithmetic mean of the daily severity score values of VMS (mild, moderate or severe) observed during the days 22 to 28 and days 78 to 84 for week 4 and week 12 respectively.

At baseline, the daily severity score is computed as $[(2 \times \text{number of moderate VMS}) + (3 \times \text{number of severe VMS})] / (\text{total number of moderate + severe VMS})$ if at least one moderate to severe VMS was recorded during the day. In case of documented absence of moderate to severe VMS during the day, the daily severity will be set to zero.

Post-baseline (days 22 to 28 [Week 4] and days 78 to 84 [Week 12]), the daily severity score is computed as $[(1 \times \text{number of mild VMS}) + (2 \times \text{number of moderate VMS}) + (3 \times \text{number of severe VMS})] / (\text{total number of mild + moderate + severe VMS})$ if at least one mild to severe VMS was recorded during the day. In case of documented absence of VMS during the day, the daily severity will be set to zero.

The daily severity score as defined above will also be recomputed for post baseline weeks as $[(2 \times \text{number of moderate VMS}) + (3 \times \text{number of severe VMS})] / (\text{total number of moderate + severe VMS})$ if at least one moderate or severe VMS is recorded during the day.

The primary efficacy variables will be expressed as the changes from baseline computed as the differences between the estimated values at week 4 or 12 and the baseline values.

The analysis including the mild VMS will be used for submission to the FDA, the analysis without the mild VMS will be used for submission to the EMA.

12.5. Analysis of Primary Efficacy Variables

All statistical tests will be supported by presenting estimates and 95% CIs for the respective treatment effects (difference to placebo). These estimates and CIs will be based on the respective statistical models used for the analysis. Since all analyses of the efficacy variables are not exploratory in nature, adjustment for multiplicity will be performed (Dunnet adjustment for the comparison of each active dose versus placebo).

The primary efficacy comparison will test the following hypotheses for each treatment arm:

- H0: The average change from baseline in the primary efficacy endpoint in the treatment arm is greater (less pronounced) or equal to the average change from baseline in the placebo arm
- H1: The average change from baseline in the primary efficacy endpoint in the treatment arm is lower (more pronounced) to the average change from baseline in the placebo arm

The two dose groups of E4 will be compared to placebo regarding the four co-primary endpoints.

A comparison between treatment arms of the change from baseline at week 1 to week 12 in the weekly frequency of moderate to severe VMS and of the change from baseline in the weekly mean severity of moderate to severe VMS will be made by using Mixed-effect Models for Repeated Measures (MMRM). The MMRM models will include treatment, week, treatment by week interaction and pooled trial centers as fixed effects and baseline as a covariate. If the pooled center effect included in the model is significant, a treatment by center interaction will be included in the model. Treatment effects will be assessed at week 4 and 12 using two separate MMRM models (one on weekly frequency and another on weekly mean severity).

The primary analysis will use the data from the ITT population. Since an MMRM model is used, missing data imputation is not necessary. Additional sensitivity analyses will be implemented in order to assess the robustness of the results. These may include sensitivity with respect to:

- An imputation of missing data (last observation carried forward [LOCF] or other)
- The modelling strategy [analysis of covariance (ANCOVA) instead of MMRM]
- Confounders (for example ethnicity, hysterectomized status)
- Populations studied (mITT, PP)
- Any combination of the above

In addition, all primary efficacy variables will be tabulated at baseline and at each post-baseline time point.

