8.1.1. Justification of Sample Size

Efficacy Study part: based on results observed for the E4 15 mg dose in the Phase 2 study, a sample size of ~200 subjects per arm provides a power of at least 80% to simultaneously achieve a superiority (upper bound of a 95% 2-sided confidence interval [CI] lower than zero) over placebo for the four co-primary endpoints together. This sample size accounts for a dropout rate during the first 12 weeks of the study of 35% and 20% for non-hysterectomized and hysterectomized women, respectively.

It is planned to enroll approximately 100 hysterectomized and 100 non-hysterectomized subjects per treatment arm.

Safety Study part: the target number of ~400 subjects has been selected to fulfill the requirement stated in International council for harmonization of technical requirements for pharmaceuticals for human use (ICH) E1 guideline (CPMP/ICH/375/95) regarding number of subjects exposed to the drug for safety assessments.

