12.6. Secondary Efficacy Variables

In addition to all the secondary efficacy endpoints previously described, all the variables described above for the assessment of the primary objectives are also considered as secondary efficacy variables when evaluated at other time points than Week 4 and Week 12.

In addition, three VMS weekly weighted scores, taking into account both the frequency and the severity of VMS, will be computed based on the diary data as:

- $[(2 \times \text{number of moderate VMS}) + (3 \times \text{number of severe VMS})]$ for baseline and post baseline visits if at least one moderate to severe VMS was recorded and zero otherwise.
- $[(1 \times \text{number of mild VMS}) + (2 \times \text{number of moderate VMS}) + (3 \times \text{number of severe VMS})]$ for baseline and post baseline visits if at least one mild to severe VMS was recorded and zero otherwise.
- $[(2 \times \text{number of moderate VMS}) + (3 \times \text{number of severe VMS})]$ if at least one moderate to severe VMS was recorded for baseline visits and $[(1 \times \text{number of mild VMS}) + (2 \times \text{number of moderate VMS}) + (3 \times \text{number of severe VMS})]$ for post baseline visits if at least one mild to severe VMS was recorded and zero otherwise.

Furthermore, the severity score will also be recomputed as $[((1 \times \text{number of mild VMS}) + (2 \times \text{number of moderate VMS}) + (3 \times \text{number of severe VMS})) / (\text{total number of mild + moderate + severe VMS})]$ if at least one mild to severe VMS is recorded during the day for baseline and post baseline visits.

In case of documented absence of moderate to severe VMS during the day, the daily severity score will be set to zero. These additional efficacy variables will be derived for every week between baseline and week 12 based on the respective 7-day periods. All VMS related secondary efficacy variables will be expressed as changes from baseline computed as the differences of the estimated values at week 1 to 12 and the baseline values.

The percentage of subjects with a CID in the weekly frequency of moderate to severe VMS at weeks 4 and 12 will be assessed according to Gerlinger et al. (31).

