12.7. Analysis of Secondary Efficacy Variables

All VMS related secondary efficacy variables will be analyzed using the same methodology as for the primary efficacy variables and will be based on the data from the ITT population.

All other secondary continuous efficacy variables will be analyzed using either an ANCOVA or an MMRM model depending on the type of endpoint considered. These models will be evaluated using data from the ITT, PP and mITT populations without imputation of data. Appropriate covariates may be included in the analyses.

The other categorical efficacy variables (scores, responder analysis) will be analyzed using appropriate statistical methods for the comparison of each treatment arm to the placebo arm.

In addition, all secondary efficacy variables will be tabulated at baseline and at each post-baseline time point.

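### Protocol 12.5 calls every efficacy analysis non-exploratory and multiplicity-adjusted, but the protocol as supplied has no control across secondary endpoints or weeks and no rule tying a dose's secondary tests to its co-primaries

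*Protocol*

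**What the plan says.** Protocol 12.5 opens its multiplicity statement with "Since all analyses of the efficacy variables are not exploratory in nature, adjustment for multiplicity will be performed", and the bracket that follows gives the procedure: "Dunnet adjustment for the comparison of each active dose versus placebo". The synopsis repeats both. No other procedure is named.

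On the secondary variables, Section 12.7 says: "All VMS related secondary efficacy variables will be analyzed using the same methodology as for the primary efficacy variables". Other continuous secondaries get ANCOVA or MMRM in the ITT, PP and mITT sets. Other categorical ones, with responder analyses given as an example, get methods that are not specified. No multiplicity procedure is attached to either group.

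The secondary list is long. Section 6.1.2 covers weekly VMS variables over 12 weeks, responder rates, hemostasis, lipids and glucose, bone markers, MENQOL and CGI. Section 12.6 adds to it: "In addition, three VMS weekly weighted scores, taking into account both the frequency and the severity of VMS, will be computed based on the diary", derived for each week.

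Exploratory objectives are listed separately in Section 6.1.3. The supplied SAP covers only the single-arm Safety Study part and marks multiplicity as not applicable (SAP 7.6.1.2). Its introduction cites a separate Efficacy Study Part SAP, version 3.0 of 5 April 2022, which is not among the documents.

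**The concern.** Dunnett deals with one source of multiplicity: two doses sharing a placebo arm, for a given endpoint at a given time. It does nothing about testing many endpoints at many weeks. A statement that all efficacy analyses are non-exploratory and adjusted therefore credits the secondary results with a property that the named procedure cannot give them.

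The protocol also lacks a rule that a dose must meet its four co-primaries before its secondary tests can support a claim. As written, a dose that fails the primary could still be credited with an early week of effect, a responder difference or a change in a bone marker.

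These results may be used. Section 7.1.3.2 gives the quality-of-life and satisfaction measures a role in identifying the best dose, Section 12.9 analyses secondary objectives 1 and 2 at the same trigger as the primary, and Section 5.3 places the results in the regulatory dossier.

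**Working it through.** The plan gives no error-rate figure for the secondaries, so there is none to reproduce. Its nearest stated figure is the power of at least 80% in 8.1.1. That cannot be recomputed, because no effect size, SD or correlation is given, and it concerns only the co-primaries.

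**Step 1: count the comparisons for each dose against placebo.** The four co-primaries are left out, and MENQOL is taken as one score.

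| Source | Rule | Count |
|---|---|---|
| 6.1.2, endpoint 1.1 | 2 variables × 12 weeks − 4 | 20 |
| 1.2 | 2 × 12 | 24 |
| 1.3 | 2 thresholds × 12 | 24 |
| 1.4 | 2 thresholds × 12 | 24 |
| 2.1 | 2 time points | 2 |
| 3.1 hemostasis | 9 × 2 | 18 |
| 3.2 lipid/glucose | 10 × 2 | 20 |
| 3.3 bone | 4 × 2 | 8 |
| 4.1 MENQOL | 1 × 2 | 2 |
| 4.2 CGI | 3 time points | 3 |
| **6.1.2 total** | | **145** |
| 12.6 weighted scores | 3 × 12 | 36 |
| **With 12.6** | | **181** |

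Of the 181, 130 are VMS-related (20 + 24 + 24 + 24 + 2 + 36) and 51 are not (18 + 20 + 8 + 2 + 3).

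Other counting rules move the total. Five MENQOL scores (total plus four domains, as in SAP 7.6.1.6.2 for the Safety part) add 8, giving 189. Counting the recomputed severity score of 12.6 as separate from endpoint 1.2 adds 12 to 181, giving 193.

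**Step 2: error rate per comparison.** The level is taken as 5% two-sided, from the criterion in 8.1.1 ("upper bound of a 95% 2-sided confidence interval"). With equal allocation the two dose contrasts have correlation 0.5. Solving P(|Z1| ≤ c and |Z2| ≤ c) = 0.95 at large degrees of freedom gives c = 2.212. The per-dose nominal p is 2 × (1 − Φ(2.212)) = 0.027. So 5% is the chance of an error for at least one dose, and 2.7% is the chance for a given dose.

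**Step 3: expected false positives under a global null, with Dunnett applied throughout.**

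- At least one dose: 181 × 0.05 = 9.05 endpoint-time points (145 × 0.05 = 7.25; 189 × 0.05 = 9.45).
- Per dose: 181 × 0.027 = 4.9, of which about half (2.4) favour E4.
- If Dunnett is confined to the 130 VMS-related comparisons and the other 51 are tested unadjusted at 5%: 130 × 0.027 + 51 × 0.05 = 3.5 + 2.6 = about 6.1 per dose.

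Correlation between tests does not change these expectations.

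**Step 4: chance of at least one false positive.** This does depend on correlation, which the documents do not give. The independence value is 1 − 0.95^181 = 0.9999. A simulation of 20,000 null trials (130 VMS and 51 other comparisons, equal correlation within each block, independent blocks, Dunnett critical value) gave:

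| Correlation within VMS | Correlation within others | At least one, either dose |
|---|---|---|
| 0.5 | 0 | 0.99 |
| 0.7 | 0.3 | 0.92 |
| 0.9 | 0.3 | 0.86 |
| 0.95 | 0.5 | 0.71 |
| 0.9 | 0.9 | 0.41 |

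All correlations are assumed. Every row is far above 5%.

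**The case against.** The strongest reply is that the analysis plan for this part of the trial has not been seen. A secondary testing order would normally sit in the Efficacy Part SAP. This stands: the point can be made only about the protocol as supplied, and a reader who concluded that the sponsor has no hierarchy anywhere would go beyond the documents. It does not remove the point, because protocol version 8.0 (21 June 2022) is later than that SAP and still carries the sentence.

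Second, the sentence sits in the section on the primary variables and may have been meant only for them. That is a fair account of the intention, but the words cover all efficacy variables. They also conflict with 6.1.3, which lists an efficacy endpoint under an exploratory objective. On the narrow reading, the remedy is still to narrow the sentence.

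Third, the size is easily overstated. A reader might infer some 190 tests per dose with 9 to 10 false positives for each dose. The documents do not support that: 189 needs five MENQOL scores that neither 6.1.2 nor 12.6 lists, and the 5% left after Dunnett is shared by both doses. Nor is a false positive near certain, since 0.9999 assumes independence and the weekly VMS variables come from the same diary. A global null is itself a worst case, because Section 5.2 reports Phase 2 effects on free protein S, SHBG and bone markers.

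Fourth, 38 of the 51 non-VMS comparisons (18 + 20) are hemostasis and lipid or glucose markers, which 7.1.3.2 treats partly as monitoring of estrogen effects. Strict adjustment there could hide harm. This stands, and it argues for reporting them as nominal rather than for adjusting them.

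**Conclusion.** The point holds for the protocol as supplied. Its multiplicity statement covers all efficacy analyses, its only procedure covers two doses, and nothing controls error across secondary endpoints and weeks or makes a dose's secondary tests conditional on its co-primaries. For the non-VMS secondaries even the dose adjustment is not stated, and for the responder analyses it is unclear.

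The size rests on 181 comparisons under the counting rule above, a 5% two-sided level, Dunnett applied throughout and a global null: about 9 endpoint-time points falsely positive for at least one dose, or about 5 per dose. The chance of at least one cannot be fixed without assuming correlations.

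A reader might also infer that the primary claim is at risk. It is not: 8.1.1 sets the aim as superiority on all four co-primaries together, so they need no further split within a dose, and Dunnett covers the two doses. The weakness lies in what may be claimed from the secondaries.

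**What to change.** First, check the Efficacy Part SAP. If it holds a secondary hierarchy, align Protocol 12.5, 12.7 and the synopsis with it. If it does not:

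- Limit the non-exploratory and multiplicity-adjusted wording to the four co-primary endpoints.
- State that a dose's secondary endpoints may support a confirmatory claim only after that dose meets all four co-primaries, and only in a short pre-specified order chosen by the sponsor. Give the level for each dose's list; half of 0.05, or 0.025 per dose, bounds the two-dose error at 0.05 with no assumption about correlation. Alternatively, state that there are no confirmatory secondary claims.
- Report all other secondary p-values as nominal.

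A flat Bonferroni correction is not a practical substitute: 0.05 / 181 is about 0.00028 per comparison.

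The cost is protocol and SAP wording and fewer confirmatory secondary claims. No extra subjects or data are needed.

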7.2. Study and Treatment Assignment

Assignment into any of the study parts (i.e. Efficacy and Safety) and treatment subgroups (15 mg, 20 mg and placebo) will be done by the Interactive Web Response System (IWRS) system (i.e cannot be done by site staff). This assignment will take into account the modified MENQOL score, frequency and severity of hot flashes, hysterectomized vs. non-hysterectomized status, and availability of places in each study part/subgroup.

Efficacy Study part

Subjects eligible for participation in the Efficacy Study part will be randomly allocated to one of the three treatment arms [E4 15 mg (Arm 1), E4 20 mg (Arm 2) or placebo (Arm 3)] in a 1:1:1 ratio using a computer-generated randomization schedule.

Safety Study part

Subjects eligible for participation in the Safety Study part will all be allocated to treatment with E4 20 mg (Arm 4).

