8. SUBJECT SELECTION AND DISCONTINUATION/WITHDRAWAL OF SUBJECTS

8.1. Source and Number

This will be a multicenter trial performed in multiple study sites in the United States of America and Canada. Subjects will be recruited by the investigator from his/her patients or will be recruited by recruitment campaigns. Subjects must seek treatment for the relief of menopausal symptoms, or subject may already be treated for menopausal symptoms and willing to discontinue their current treatment.

All investigators must keep a record of subjects who were considered for enrollment and were consented, but were never enrolled e.g., subject screening log to address concerns over selection bias.

This trial will enroll a total of approximately 1,000 subjects; ~600 subjects ~200 per treatment arm) in the Efficacy Study part and ~400 subjects in the Safety Study part of the trial. Enrollment will stop when the minimum required number of subjects in each study group and study part is enrolled.

The number of completers after three months of treatment in the Efficacy Study part is anticipated to be around 435, anticipating a drop-out rate of 35% and 20% for non-hysterectomized and hysterectomized women, respectively. The number of completers after 12 months of treatment is anticipated to be ~300, anticipating a drop-out rate of 50% after one year of treatment.

The number of completers in Safety Study part after 12 months of treatment is expected to be ~200, anticipating a drop-out rate of 50%.

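### The Dunnett adjustment in protocol 12.5, most naturally read as single-step, is valid, but a dose-level step-down would give more power to confirm the second dose at the same nominal familywise error

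*Protocol*

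**What the plan says.** Protocol 12.5, repeated in the Synopsis, states that "adjustment for multiplicity will be performed (Dunnet adjustment for the comparison of each active dose versus placebo", and that "The two dose groups of E4 will be compared to placebo regarding the four co-primary endpoints". The alternative hypothesis points one way: "The average change from baseline in the primary efficacy endpoint in the treatment arm is lower (more pronounced" than under placebo. Neither place says whether the Dunnett test is single-step or step-down, or whether it applies within each endpoint or to the decision on a dose as a whole. Section 12.5 also asks for an estimate and a 95% CI with every test, without saying whether the CIs are simultaneous.

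Section 8.1.1 defines success as "superiority (upper bound of a 95% 2-sided confidence interval [CI] lower than zero", to be reached "over placebo for the four co-primary endpoints together". It states that "a sample size of ~200 subjects per arm provides a power of at least 80" per cent, based on Phase 2 results for 15 mg, and does not mention the Dunnett adjustment. Section 7.2 randomizes "in a 1:1:1 ratio using a computer-generated randomization schedule".

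The supplied SAP covers only the Safety Study part and marks multiplicity as not applicable (7.6.1.2). Its introduction cites an Efficacy Study part SAP, version 3.0, which was not supplied.

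**The concern.** Under single-step Dunnett each dose must reach |z| of about 2.212 (two-sided p≤0.027) on all four co-primaries, even after the other dose has already won. Once one dose has been shown superior on all four, the only dose-level null left to protect is that of the other dose, and it can be tested at the ordinary 5% level. Holding it to 2.212 costs power for that dose.

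This matters because 7.1.3.3 gives the comparison of 15 mg and 20 mg as a reason for the design. If 20 mg is the stronger dose, the power is lost mainly on 15 mg.

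**Working it through.** **Inputs from the protocol.** Two doses against one placebo arm, four co-primaries that must all be met, 1:1:1 allocation, two-sided 95% level (0.025 in the direction of benefit), about 200 per arm, power of at least 80%.

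**The plan's own figures.** The 80% cannot be reproduced, because no mean differences, SDs or endpoint correlations are given for the four endpoints. The completer count in 8.1, which rests on "anticipating a drop-out rate of 35% and 20% for non-hysterectomized and hysterectomized women, respectively", does reproduce: 300 × 0.65 + 300 × 0.80 = 195 + 240 = 435, or 145 per arm.

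**Critical values.** With a shared placebo and equal arms, the correlation between the two dose contrasts on one endpoint is (σ²/n)/(2σ²/n) = 0.5. Solving P(|Z₁|≤c, |Z₂|≤c) = 0.95 at that correlation (large sample) gives c = 2.212, per-comparison p = 0.0270. The unadjusted value is 1.960.

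**Procedures compared.**
- Single-step: a dose wins if all four z exceed 2.212.
- Dose-level step-down: a dose wins if all four z exceed 2.212, or if all four exceed 1.960 and the other dose has won all four at 2.212.

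**Familywise error by reasoning.** The step-down declares some dose a winner exactly when single-step does, because the second step opens only after a single-step win. With both doses null, the familywise error is therefore identical. With one dose null, its error is at most P(z > 1.960) = 0.025.

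**Familywise error by calculation** (benefit direction, nominal 0.025; each null dose is null on one endpoint and clearly effective elsewhere; endpoint correlation 0 to 0.8):

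| Configuration | Single-step | Step-down by dose | Step-down endpoint by endpoint |
|---|---|---|---|
| Both null, same endpoint | 0.025 | 0.025 | 0.025 |
| Both null, different endpoints | 0.026-0.027 | 0.026-0.027 | 0.047-0.049 |
| One dose null | about 0.0135 | 0.025 | 0.025 |

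The slight excess over 0.025 in the second row arises because contrasts on different endpoints correlate below 0.5. It is the same for single-step and dose-level step-down. Endpoint-wise stepping fails there because each dose, effective on the endpoint where the other is null, opens the 1.960 test for it.

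**Power.** Assumptions: equal standardized effects on all four endpoints and in both doses, and a common endpoint correlation r. The noncentrality δ is solved from P(all four Z + δ > crit) = 0.80, followed by simulation with 1,000,000 draws per case. Each cell gives single-step → dose-level step-down.

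| 80% anchored at | r | δ | Per dose | Both doses | At least one |
|---|---|---|---|---|---|
| 1.960 | 0.3 | 3.49 | 70% → 76% | 55% → 67% | 86% → 86% |
| 1.960 | 0.5 | 3.41 | 71% → 76% | 56% → 67% | 86% → 86% |
| 1.960 | 0.8 | 3.22 | 72% → 77% | 58% → 68% | 86% → 86% |
| 2.212 | 0.3 | 3.74 | 80% → 85% | 68% → 78% | 92% → 92% |
| 2.212 | 0.5 | 3.66 | 80% → 85% | 68% → 78% | 92% → 92% |
| 2.212 | 0.8 | 3.47 | 80% → 84% | 68% → 77% | 92% → 92% |

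At r = 0.9 the figures are 72% → 77% and 58% → 68% with the first anchor, and 80% → 84% and 69% → 77% with the second. If 20 mg has a 15% larger effect (first anchor, r 0.3 to 0.9), power for 15 mg goes from 70-72% to 78%, and for both doses from 65-66% to about 75%.

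**The case against.** The other side has several good points.

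- **Single-step is an inference.** The text says only Dunnett. The Efficacy SAP may specify a step-down. This stands.
- **Single-step is a standard, valid choice.** It also has simultaneous CIs that match its tests, which suits a plan that wants a CI with every test and defines superiority by a CI bound. This stands; the point is one of efficiency.
- **Single-step is stricter in one case.** With one null dose its error is 0.0135 against 0.025. A reader might infer that step-down costs nothing in error. The exact statement is that it uses the nominal level where single-step stays below it.
- **The overall chance of success does not move.** The first step is the same test, so P(at least one dose) is unchanged, and the protocol claims no power for confirming both doses. This stands and limits the benefit to the second dose.
- **The 70-72% baseline is conditional.** A reader might infer that the trial is underpowered against its stated 80%. That holds only if the 80% was computed without Dunnett. Section 8.1.1 cites a 95% CI and says nothing either way, so the documents do not support that conclusion.
- **The rule does not carry over to the secondary endpoints.** Section 12.7 applies the primary methodology to all VMS-related secondary variables, where a gate on four co-primaries has no meaning. This stands and is handled in the fix.

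**Conclusion.** The point holds as an efficiency improvement, not as an error in the plan. If 12.5 means single-step, a dose-level step-down rejects everything it rejects and sometimes more, at the same nominal familywise level. Under the equal-effect assumptions and endpoint correlation 0.3 to 0.9, the gain is about 4 to 6 percentage points per dose and 9 to 12 points for both doses, across the two readings of the 80%. Its direction does not depend on those assumptions; its size does, because the protocol gives no SDs or endpoint correlations.

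It would go too far to say that the plan's test is invalid, that it is definitely single-step, or that any step-down is safe. Stepping down within each endpoint can nearly double the dose-level error.

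**What to change.** Before the Visit 4 analysis is unblinded, amend 12.5, the Synopsis and, if it is not already there, the Efficacy SAP to state:

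1. A dose wins only if all four co-primaries are significant in favour of E4.
2. For each dose take the largest of its four two-sided p-values. Test the dose with the smaller maximum at the Dunnett level (p≤0.027).
3. Only if that dose wins all four, test the other dose on all four at unadjusted two-sided 5%. Otherwise stop.
4. Step by dose, never endpoint by endpoint.
5. The gate applies only to the four co-primaries. Section 12.7 needs its own statement for the secondary VMS variables.
6. The unadjusted 95% CIs are for estimation. Superiority is decided by the step-down rule, not by the CI bound in 8.1.1.

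Apply the rule once with the severity score for the FDA and once with that for the EMA (12.4).

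**Cost.** A short text change, made as a formal amendment under 13.5, with no extra subjects. The downside is that no simple simultaneous CIs match the test. If the better dose has a largest p-value between 0.027 and 0.05, all four of its unadjusted CIs exclude zero although it formally fails. The text should say so in advance.
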